8.3.7 Overall survival

Overall survival is defined as the time from start of treatment until death due to any cause. If patient is still alive at the time of analysis, OS will be censored on the date of last known being alive.

8.4 Safety/tolerability

Analyses of safety/ toxicity will be performed for all patients having received at least one dose of study drug. The study will use the CTCAE version 4.03 for reporting of adverse events (http://ctep.cancer.gov/reporting/ctc.html).

9. BIOMARKER, CORRELATIVE, AND SPECIAL STUDIES

9.1 Overview

The major hypothesis of our correlative studies are that:

- 1) Treatment with entinostat will result in changes in TME enhancing T cell effectors and/or reducing suppressive ability of CD4+FoxP3+ T regulatory cells and MDCSs in the tumors.
- 2) Immunologic changes in biopsy specimens will correlate with subsequent clinical response to anti-PD-1/PD-L1 therapy.

Explorative correlative studies will be performed on biopsy specimens (pre - and post- entinostat treatment and approximately after 6 weeks from Cycle 1 day 1) and blood samples.

Mandatory research bloods and tumor biopsies will be obtained at baseline (day -14), after two weeks of entinostat lead in period (on approximately day 14 from the first entinostat administration), and approximately after 6 weeks from Cycle 1 day 1 visit. (see Study Calendar, **Section 10**). Biopsies at progression are optional.

These three mandatory biopsies will provide valuable information regarding the mechanism of action of entinostat and the impact on the TME when PD1 inhibition is added in, as well as primary resistance mechanisms to the strategy.

NOTE: All samples will be collected as outlined below, initially processed, and stored/bank until future analysis.

9.2 Collection of Specimens

9.2.1 Tissue Samples

Mandatory and optional tumor biopsies will be obtained at the time points as outlined above and on the Study Calendar.

Subjects will undergo a direct or image-guided research biopsy procedure. FNA and on-site cytopathologic evaluation, where appropriate, will be done for sample/site adequacy followed by

core biopsies for collection of tissue for the research correlates outlined. The biopsy site will be clearly documented in the records; baseline and each follow-up biopsy will preferentially be done in the same organ site.

Approximately six (6) core biopsy specimens will be obtained with each biopsy as outlined; the cytopathology slide will also be retained and submitted, if performed. Up to three cores will be placed in formalin solution and paraffin embedded. The remaining biopsy specimens will be flash frozen in liquid nitrogen and then stored as fresh tissue at \leq -70°C for extraction of DNA and RNA. The biopsy specimens will be stored and batch shipped at the latest at the conclusion of study enrollment.

The study staff will be notified when a biopsy is taking place. If core biopsy is not possible, other methods may be approved in advance by the IND Sponsor/designee.

If a subject discontinues the study prior to a planned follow-up biopsy, an attempt should be made to collect the next scheduled biopsy when the decision is made to discontinue and prior to initiation of additional treatment, if possible.

In the event that a subject cannot undergo a second biopsy for any reason, including refusal, or the baseline biopsy was unsuccessful or invaluable, the second and the third biopsies, as well as the optional biopsy at the time of progression, will not be required and the subject will continue to be treated per study protocol.

NOTE: Archival tumor specimens from previously collected samples will be obtained for correlative analysis, if available.

Biopsy Instructions

Acceptable biopsy sites are:

- Percutaneous biopsy of deep sites with local anesthetic and/or sedation (with an expected risk of severe complications < 2%)
- Cutaneous biopsy of palpable sites with local anesthetic and/or sedation with an expected risk of severe complications < 2%
- No open surgical or laparoscopic procedures will be performed solely to obtain a biopsy for this protocol.

Such biopsies can be safely performed as evidenced by literature reports [122, 123], as well as, in the prior experience of our PI at the NIH Clinical Center [124], where, among 244 research tumor biopsies (18G needle) in liver (126), subcutaneous/chest wall/abdominal wall (36), intramuscular (18), lung and lymph nodes, there were 8 minor cases of bleeding, and one pneumothorax requiring 48h hospitalization (21). This evidence support that serial percutaneous core-needle biopsies can be obtained safely yielding material applicable for multiple translational applications.

Considering the tumor histologies to be enrolled in this study are pancreatic cancer and cholangiocarcinoma, biopsies will probably be of liver. In our institution, the expected complication rate of percutaneous liver biopsy similar to those that will be done for this trial is less than 1 %. Risks of the procedure include, but are not limited to, bleeding, infection, pain, and scarring.

9.2.2 Blood Samples

Whole blood for PBMCs (up to 180cc) will be collected at the specified timepoints (See Section 10). Detailed instructions for blood collection, processing, and storage are provided in the Laboratory Manual.

Sera (up to 10 cc) and plasma (up to 20cc) will be collected at the specified timepoints (See Section 10). Detailed instructions for blood collection, processing, and storage are provided in the Laboratory Manual.

In the event that a subject cannot have all blood samples or volume needed at a single visit, the samples and/or remaining samples should be collected at the next possible visit.

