4. TREATMENT PLAN

4.1 Agents Administration

Treatment will be administered on an outpatient basis. Reported adverse events and potential risks are described in **Section 6**. Appropriate dose modifications are described in **Section 5**.

No investigational or commercial agents or therapies other than those described below may be administered with the intent to treat the patient's malignancy.

The cycle length is 28 days. Treatment will consist of the combination of entinostat and nivolumab. A lead-in of entinostat 2 weeks prior to combination therapy at the dose of 5 mg/weekly, will be incorporated to help determine the effect of entinostat on immune-related parameters in tumor biopsies.

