Female subject of childbearing potential should have a negative urine or serum pregnancy test within 72 hours prior to receiving retreatment with study medication. NOTE: If a patient has a positive or indeterminate serum or urine pregnancy test, then an ultrasound must be done to rule out pregnancy to enroll on trial. A serum B-HCG value of <25 is considered a negative pregnancy test.

- ^{14.} Radiologic imaging of chest/abdomen/pelvis (CT preferred, abdominal/pelvis MRI will be performed for patients with CT contrast allergy) and any other imaging required per RECIST for the particular subject are required at baseline. A baseline bone scan or PET/CT could be required to assess bone disease in patients with suspected or known bone metastases. A baseline brain CT scan or MRI is requested in patients with suspected or known brain metastases. Repeat same modality(ies) in follow-up to follow known site(s) of disease, with other assessments as clinically indicated if one has not been done within the past 6 weeks.
- ^{15.} Entinostat is to be self-administered by the patient weekly.
- ^{16.} Patients will receive entinostat 5 mg oral once a week plus nivolumab 240 mg every two weeks for approximately four months. After 4 months (16 weeks), nivolumab will be given at a dose of 480 mg fixed dose every 4 weeks. Therapy may continue with entinostat 5 mg weekly plus nivolumab 480 mg every 4 weeks, until intolerance or progression.

- ^{17.} Blood for serum and plasma samples will be collected at baseline (D -14), after entinostat lead in (on approximately day 14 (D-1) of entinostat therapy), on week 6, prior to dosing on C2D15, and at the time of the EOT visit. Detailed instructions for blood collection, processing, and storage are provided in the Laboratory Manual.
- ^{18.} Mandatory fresh tissue samples will be collected at D-14 and after entinostat lead-in (on approximately day 14 (D-1) of entinostat therapy prior to dosing on C1D1) and on week 6, prior to dosing on C2D15. A ± 3 day window applies to both time points. All

J1798/Version 5.0/May 21, 2020

samples are collected pre-dose on treatment days). Approximately six (6) core biopsy specimens will be obtained with each biopsy as outlined; the cytopathology slide will also be retained and submitted, if performed (See Section 9.2.1) All

correlative blood/tissue studies should be performed on the same day.

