NOTE: If applicable, the daily dose of entinostat may occur prior to hematology/chemistry tests and these laboratory tests may be drawn at the same time as the correlative blood samples.

- ^{19.} A third mandatory biopsy will be performed at week 6 from Cycle 1, Day1. A window of +14 days applies to this time point
- ^{20.} An optional biopsy will be performed at the time of disease progression.
- ^{21.} Archival tumor specimens from previously collected samples will be obtained for correlative analysis, if available.
- ^{22.} Weekly assessments for toxicity/adverse events may occur by phone on days when entinostat alone is administered. Additionally, assessments are to continue for 30 days after the last dose of nivolumab (at intervals <21 days) or to resolution of drug-related AEs to \leq Grade 1, whichever occurs later. SAEs that occur within 100 days of the last treatment or before initiation of a new antineoplastic treatment should also be followed and recorded. These may occur by phone for subjects no longer being seen at the institution; however, an in-person clinic visit may be needed to confirm event resolution and/or to effectively evaluate possible immune-related events. Subjects must be told of follow-up requirements at study entry.
- ^{23.} Subjects who complete or discontinue from treatment because of progression disease will be followed (by phone or email) every three months (+/- 2 weeks) after completion of the EOT visit for up to 2 years or study closure to monitor overall survival. Information of other cancer therapies after discontinuation from the study treatment will also be collected.

For subjects who discontinue treatment for reasons other than tumor progression, will be contacted (by phone or email) every three months (+/- 2 weeks) after completion of the EOT for up to 2 years or study closure to monitor overall survival, and information

93

about disease status will be also collected if possible (i.e. radiological imaging and/or tumor markers) until documented tumor progression.

NOTE: For evaluation of PFS, all subjects who discontinue study drug administration prior to 6 months must have restaging scans/imaging within a 7 day window of the 6 month time point from the date of initiation of combination treatment

J1798/Version 5.0/May 21, 2020

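### Make-up blood draws and the baseline biopsy window are not tied to first dosing, so some exploratory samples can carry the wrong drug exposure

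*Combined protocol and SAP*

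**What the plan says.** Section 4.1 adds a two-week entinostat lead-in that "will be incorporated to help determine the effect of entinostat on immune-related parameters in tumor biopsies". Section 9.1 extends the before-and-after comparison to blood as well as biopsies. Objective 1.3.4 and endpoint 1.6.3 (circulating suppressor cells) rest on blood alone; endpoint 1.6.1 uses both.

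**Blood.** Footnote 17 of the Study Calendar sets draws at Day -14, about Day -1, week 6 and end of treatment. It attaches a pre-dose condition only to the week 6 (C2D15) draw. For a draw that cannot be completed at one visit, Section 9.2.2 says "the samples and/or remaining samples should be collected at the next possible visit".

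**Tissue.** Footnote 18 schedules biopsies at Day -14, after the lead-in and at week 6, the last two "of entinostat therapy prior to dosing on C1D1) and on week 6, prior to dosing on C2D15". It adds "A ± 3 day window applies to both time points" and says that "samples are collected pre-dose on treatment days". It also asks for correlative blood and tissue on the same day. Footnote 19 gives week 6 its own +14-day window.

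**Note under footnote 18.** Entinostat may be taken before the hematology and chemistry tests, and "these laboratory tests may be drawn at the same time as the correlative blood samples".

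**The concern.** The lead-in separates the two drugs only if the first sample is untreated and the second has seen entinostat but not nivolumab. The make-up rule sets its limit by visit, not by exposure. A site that follows it literally can file blood taken after entinostat as baseline, or blood taken after nivolumab as post-lead-in. The baseline biopsy window has a similar gap.

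Section 12.3.4 does not say how to handle a sample whose actual exposure differs from its nominal time point. If such samples were analysed as labelled, a late baseline would pull the entinostat effect toward zero, and a late post-lead-in sample would credit entinostat with part of the effect of nivolumab. An untreated sample cannot be recovered once dosing has begun.

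**Working it through.** The documents give no figure for late draws, so there is none to reproduce. The check maps each rule onto study days and then sizes the effect under stated assumptions.

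**Day map.** Footnotes 17 and 18 equate entinostat day 14 with Day -1, so there is no Day 0. Then Day -14 is entinostat day 1, Day -11 is day 4, Day -7 is day 8, C1D1 is day 15 and C1D15 is day 29. Entinostat is given on Day -14 and Day -7. The first nivolumab dose is on C1D1.

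**Blood meant for Day -14.** In Table 10.1, Day -7 has entinostat and a toxicity check but no blood test, and Section 10 allows phone contact in entinostat-only weeks. The next scheduled visit with blood tests is C1D1, after two entinostat doses and on the visit of the post-lead-in draw. If Day -7 were used instead, the draw would fall on entinostat day 8.

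**Blood meant for Day -1/C1D1.** The next visit with blood tests is C1D15, 14 days after the first nivolumab dose. A draw there before that day's infusion satisfies the pre-dose sentence in footnote 18, yet the patient has already had nivolumab.

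**Are short draws plausible?** Section 9.2.2 asks for up to 180 + 20 + 10 = 210 cc per time point and itself provides for incomplete draws.

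**Baseline biopsy.** Day -14 ± 3 runs from Day -17 to Day -11. Unless dosing moves with the biopsy, Days -13 to -11 follow the first dose. They are not treatment days, so the pre-dose sentence does not reach them.

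**Post-lead-in biopsy.** Day -1 ± 3 would run from Day -4 to C1D3, but footnote 18 already requires this biopsy before C1D1 dosing. There is no gap here.

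**Size, baseline drawn late.** Let f be the share of pairs with a late baseline and g the share of the entinostat effect already present in it. The fraction of the true mean contrast retained is 1 − f × g.

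- f = 0.05, g = 0.25: 1 − 0.0125 = 0.988
- f = 0.10, g = 0.50: 1 − 0.05 = 0.95
- f = 0.20, g = 1: 1 − 0.20 = 0.80

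Both f and g are assumed. For scale, 1, 3 or 5 affected pairs among 27 subjects in a cohort give f = 3.7%, 11.1% or 18.5%. A whole baseline made up at C1D1 has g = 1, so that pair shows no lead-in change.

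**Size, post-lead-in blood drawn late.** If nivolumab and the extra entinostat weeks add h to the marker, the mean lead-in change shifts by f × h, with f now the share of late post-lead-in draws. The later change (post-lead-in to combination) loses the same amount. The documents give no value for h, so neither size nor sign can be stated.

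**The case against.** The strongest reply is that the intended timing is clear. Section 9.1 describes the specimens as taken before and after entinostat. The Day -14 column of Table 10.1 carries an asterisk meaning within 7 days before the first entinostat dose. Footnote 18 adds pre-dose and same-day rules. Collection details are left to a Laboratory Manual that is not among the documents and may limit make-up draws. This shows intent, but it does not close the gap: the entinostat dosing row sits in the same asterisked column, and none of these rules says how a late draw is to be classified. If the manual does set a limit, Section 9.2.2 still needs to agree with it.

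Other parts of the reply stand and limit the point. The make-up rule covers blood only, while Section 4.1 states the purpose of the lead-in in terms of biopsies. Section 9.2.1 has no matching rule for tissue; after a failed baseline biopsy the later ones are not required. A short draw still leaves genuine Day -14 material, so only the made-up portion is affected.

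A reader might also infer that the note under footnote 18 openly permits post-dose correlative blood. That goes too far. It lets entinostat precede safety tests and says those tests may share a draw with the correlative blood. It can be read consistently with the pre-dose rule, although it is loose: it speaks of a daily dose of a weekly drug. The two texts need reconciling, but a definite contradiction is not shown.

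**Conclusion.** The concern holds in a limited form. As written, Section 9.2.2 allows baseline blood to be made up after entinostat and post-lead-in blood after nivolumab, and footnote 18 sets no explicit pre-first-dose limit for the Day -14 biopsy. The exposed contrasts are exploratory: for blood, 1.3.4, 1.6.3 and part of 1.6.1; for tissue, those that use the baseline biopsy.

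Two stronger readings are tempting and not supported. The first is that the ±3-day window lets post-lead-in biopsies follow nivolumab; footnote 18 rules this out. The second is that the lead-in contrast is erased. That would need f × g = 1, meaning every baseline late and carrying the full effect. The realistic consequence is dilution or misattribution in the affected pairs.

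Its size is unknown, because it depends on how many draws are late. The 80-99% range for the retained contrast rests wholly on assumed f and g. No primary or secondary analysis, and no sample-size figure, changes. Priority: minor.

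**What to change.** - **Section 9.2.2:** a missed or short Day -14 draw may be completed only before the first entinostat dose, and a Day -1 draw only before C1D1 dosing. Otherwise the sample counts as missing for that time point.
- **Footnote 18:** close the baseline window at the first entinostat dose, and say which two of the three listed time points the ±3 days covers.
- **Data collection and Section 12.3.4:** record actual draw time relative to each drug's dosing, and leave wrongly exposed samples out of the paired contrast.
- **Note under footnote 18:** reconcile it with the pre-dose rule in that footnote.
- **Laboratory Manual:** check that it says the same.

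The cost is wording in the protocol and, if needed, the manual. The downside is that a few samples become missing instead of late. These are limits on sample collection and do not alter dosing.

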9.2.3 Handling and Shipping of Specimens

A unique subject identifier will be assigned to each subject by the coordinating center and will be used to label the samples. The protocol scientific investigator(s) analyzing the samples will be blinded as to the direct subject identifiers.

A **Laboratory Manual** will be provided for specific handling and processing instructions; this document will be disseminated with the clinical protocol and is also available to investigators on request from the Coordinating Center.

After shipping, samples, and associated data, will be stored at Johns Hopkins unless the subject withdraws consent.

9.3 Methods

9.3.1 Immunohistochemistry (IHC) and Gene Array Analyses

The density of CD8⁺ Teffs, PD-1+, FoxP3⁺ Tregs, and the number of MDSCs will be evaluated by IHC in tumor specimens. Human PD-L1 IHC staining of paraffin embedded tumor specimens will be done using the Dako Catalyzed Signal Amplification system [126]. The density of cells will be determined at the junction between tumor tissue and non-tumor tissue (invasive front) and within the tumor (TILs). The densities will be reported as positive cells / mm² of tissue using digital analysis. Each slide will be digitally scanned at 20X magnification and areas to be analyzed will be indicated using Aperio software. PD-L1 expression is considered positive if membranous staining is present in more than 5% of the neoplastic cells [127]. In addition, immune aggregates will be microdissected and evaluated for immune signatures using gene array analyses. These studies will be conducted as previously described [128].

9.3.2 Next Generation Sequencing (NGS)

Tumor specific somatic mutations will be identified by whole-exome sequencing (WES) using DNA isolated from tumor tissue, along with subject-matched normal lymphocytes. Genomic DNA from tissue and lymphocyte sample will be sonicated to a modal size of 200 bp and ligated to Illumina TruSeq adaptors with barcodes, and subjected to minimal amplification. The resulting libraries will be subjected to selection of all exonic sequences in the genome via hybrid-capture with 120 bp biotinylated RNA-baits using the Agilent SureSelect platform. Enriched exonic sequences will be further amplified and subject to massively parallel sequence-by-synthesis 100x100 bp paired end sequencing on an Illumina HiSeq 2000 at a minimal depth of 75x average coverage. The resulting reads will be aligned to the genome using bowtie2 and variants will be called on each sample compared to the human reference using the GATK software. Somatic variants will be identified using the strelka software.

The T cell repertoire in TILs will be evaluated in tumor specimens using Adaptive Biotechnologies' next-generation sequencing-based approach.

9.3.3 HLA-Binding Prediction Algorithms and Elispot Assays

Quantification of tumor neoantigen-specific CD8⁺ T cell levels in PBL: Each of the somatic missense mutations identified by WES will be screened for potential HLA class I-binding neoepitopes using the predictive algorithm NetMHC. 19mer peptides will be synthesized spanning each mutation predicted to generate a neoeptiope; and used in IFN ELISPOT assays to measure neoepitope-specific CD8⁺ T cell levels in PBL.

9.3.4 MDSC Analysis

Levels of granulocytic and monocytic MDSCs in peripheral blood will be evaluated by 6-color fluorescence-activated cell sorting (FACS) using monoclonal antibodies specific to CD11b, CD14, CD15, CD33, HLA-DR and the IL-4 receptor.

10. STUDY CALENDAR

Notations/reminders for all calendars:

- Baselines assessments are to be conducted within 28 days of registration unless otherwise noted.
 □ Correlative blood and tissue sample participation is mandatory.
- Additional tests may be performed at the discretion of the treating investigator as per routine practice, or as otherwise clinically indicated.

The schedule should be followed as closely as is realistically possible; the schedule may be modified due to problems such as scheduling delays or conflicts (e.g., clinic closure, vacations, etc.) with the guidance of the IND Sponsor/designee, as appropriate, and will not be reportable as a deviation unless the endpoints of the study are affected.

- * Required \leq 7 days prior to the first dose of entinostat
- ** Required assessment windows during combination treatment for each cycle as noted (e.g., Days 1 and 15 is 3 days, weekly is ±1 day). Assessments on Days 1 and 15 should be completed/reviewed prior to planned nivolumab administration.

- *** After 4 months, nivolumab will be given at a dose of 480 mg fixed dose every 4 weeks (maintenance phase). Therapy may continue with entinostat 5 mg weekly plus nivolumab 480 mg every 4 weeks, until intolerance or progression.
- Patients will be assessed in clinic on D1 of every cycle, and will be contacted by phone weekly, on the weeks entinostat alone is self-administered at home.

Required \leq 14 days prior to the first dose of entinostat

NOTE: All timeframes noted after the lead-in phase refer to duration on combination treatment (e.g., first-restaging should occur after 8 weeks of initiation of combination treatment of entinostat and nivolumab.)

Table 10.1 Study Calendar

						cycle ** = 28 days)			Maintenance Phase		
Procedure	Baseline ¹	Lead-In Day -14*	Lead-In Day -7	Day 1 (±3 days)	Day 8 (±1 day)	Day 15 (±3 days)	Day 22 (±1 days)	Week 6 (+14 days)	Every 4 weeks, Beginning on week 16***	Every 8 weeks (±7 days) ²	EOT ³ 28 days After Last Dose (±7 days)
Informed Consent & Review of Eligibility Criteria	Х										
Medical History & Demographics	Х										
Physical Exam ⁴	X	X#		X				X	X		Х
Vital Signs, Height (only baseline), Weight	х	x		х				X	X		х
ECOG Performance Status	Х	х		х		X		X	Х		х
Oxygen Saturation	Х			х		X		Х	X		Х
Hematology Panel ⁵	Х	x		х		X		х	X ⁶		Х
Chemistry Panel ⁷	X	X		X		X		X	Х		Х
Coagulation Panel ⁸	X										
Thyroid Function ⁹	х			х		х		x	X		х
Hepatitis Serologies ¹⁰	х										
Electrocardiogram (ECG) ¹¹	Х										

						cycle ** = 28 days)			Maintenance Phase		
Procedure	Baseline ¹	Lead-In Day -14*	Lead-In Day -7	Day 1 (±3 days)	Day 8 (±1 day)	Day 15 (±3 days)	Day 22 (±1 days)	Week 6 (+14 days)	Every 4 weeks, Beginning on week 16***	Every 8 weeks (±7 days) ²	EOT ³ 28 days After Last Dose (±7 days)
Urinalysis ¹²	X										
Pregnancy test/ Assessment WOCBP ¹³	х	X*		X					X		
Tumor Assessments Imaging ¹⁴	Х									X	X ²⁰
CA19-9		X*								x	X ²⁰
Entinostat ¹⁵		x	X	Х	X	Х	х	х	Х		
Nivolumab ¹⁶				х		х		х	Х		
Peripheral blood for PBMC (up to 180cc) ¹⁷		X		х				Х			Х
Peripheral blood for plasma (up to 20cc) ¹⁷		х		х				Х			Х
Serum (up to 10cc) ¹⁷		Х		Х				X			Х
Fresh Tumor Biopsy ¹⁸		х		X ¹⁸				X ¹⁹			X ²⁰
Archival Tumor Sample ²¹	X										
Concomitant Medication Review	X	X		X		X		X	X		X
Symptom/Toxicity Assessment ²²			X	Х		X		X	X ²²		Х

						cycle ** = 28 days)			Maintenance Phase		
Procedure	Baseline ¹	Lead-In Day -14*	Lead-In Day -7	Day 1 (±3 days)	Day 8 (±1 day)	Day 15 (±3 days)	Day 22 (±1 days)	Week 6 (+14 days)	Every 4 weeks, Beginning on week 16***	Every 8 weeks (±7 days) ²	EOT ³ 28 days After Last Dose (±7 days)
Follow-up/Survival ²³											X ²⁴

Study Calendar: Entinostat and Nivolumab

- Baseline evaluations should occur within 28 days prior to registration, unless otherwise noted. NOTE: No window applies to demographics, informed consent, or height at baseline. If any assessments are repeated after registration and prior to dosing on Day -14, subjects must maintain eligibility requirements in order to initiate therapy. Biopsies should be performed only after patient is deemed eligible and registered on the trial.
- ² Disease assessments will be conducted every 8 weeks (+/- 1 week) from Cycle 1 Day1 for the first 6 months; this timeframe may then be extended to every 12 weeks (+/- 1 week) at the discretion of the treating provider.
- ³ A mandatory End of treatment (EOT) visit should be performed 28 days (± 7 days) after the last dose of entinostat to determine patients' safety outcome. Repeat any physical or laboratory assessments after the last dose of any study treatment if last assessment >7 days prior.
- ^{4.} Complete physical exam will be completed at baseline; focused physical examinations may be conducted thereafter.
- ^{5.} Hematology Panel includes at a minimum: basophils, eosinophils, hematocrit, hemoglobin, lymphocytes, monocytes, neutrophils, platelet count, and total white cell count.
- ⁶ Patients receiving entinostat in the maintenance phase will have hematology panel (as defined above) checked every two weeks (either in clinic or at home). When done at home, patients will be instructed to send the results to the study team and will communicate the results via fax to the study team
- ^{7.} Chemistry panel includes (if possible): albumin, alkaline phosphatase, total bilirubin [nitrogen if total bilirubin is ≥2xULN (and no evidence of Gilbert's syndrome) then fractionate into direct and indirect bilirubin)], bicarbonate, BUN, calcium, chloride, creatinine, glucose, potassium, total protein, SGOT [AST], SGPT [ALT], sodium, LDH, magnesium, amylase and lipase.
- 8. INR (international normalized ratio), PT (prothrombin time) and PTT (partial thromboplastin time) required at screening and within 30 days of image-guided research biopsies. If patient receives a biopsy at disease progression, the coagulation panel must be completed within 30 days prior to biopsy.

[figure not shown]
- ^{9.} Thyroid function will be assessed by TSH (Thyroid Stimulating Hormone) at baseline and prior to each dose of nivolumab. If abnormal, Free T3 (triiodothyronine) and T4 (thyroxine) should be assessed.
- ^{10.} The following should be assessed at baseline: Hepatitis B surface antigen (HBV sAg) and Hepatitis C antibody (HCV Ab) or Hepatitis C RNA (HCV RNA).
- ^{11.} An ECG is required during screening (prior to starting study treatment), as well as at any other time point when clinically indicated. All 12-lead ECGs should be recorded while the subject is in the supine position. The same method of assessment should be used throughout the study. Twelve-lead ECGs will be obtained after the subject has been resting in a supine position for at least 5 minutes.
- ^{12.} Bilirubin, blood, glucose, ketones, pH, protein, specific gravity, color and appearance. Microscopy should be used as appropriate to investigate white blood cells and use the high power field for red blood cells
- ^{13.} For WOCBP (women of childbearing potential) only. A serum or urine pregnancy testing is required prior to study enrollment/registration, ≤7 days prior to the first dose of entinostat and <24 hours prior to the first dose of nivolumab. After the first dose of nivolumab, an interim history to evaluate any risk of exposure to a fetus must be done prior to each dose in lieu of routine HCG testing, if appropriate.

Female subject of childbearing potential should have a negative urine or serum pregnancy test within 72 hours prior to receiving retreatment with study medication. NOTE: If a patient has a positive or indeterminate serum or urine pregnancy test, then an ultrasound must be done to rule out pregnancy to enroll on trial. A serum B-HCG value of <25 is considered a negative pregnancy test.

- ^{14.} Radiologic imaging of chest/abdomen/pelvis (CT preferred, abdominal/pelvis MRI will be performed for patients with CT contrast allergy) and any other imaging required per RECIST for the particular subject are required at baseline. A baseline bone scan or PET/CT could be required to assess bone disease in patients with suspected or known bone metastases. A baseline brain CT scan or MRI is requested in patients with suspected or known brain metastases. Repeat same modality(ies) in follow-up to follow known site(s) of disease, with other assessments as clinically indicated if one has not been done within the past 6 weeks.
- ^{15.} Entinostat is to be self-administered by the patient weekly.
- ^{16.} Patients will receive entinostat 5 mg oral once a week plus nivolumab 240 mg every two weeks for approximately four months. After 4 months (16 weeks), nivolumab will be given at a dose of 480 mg fixed dose every 4 weeks. Therapy may continue with entinostat 5 mg weekly plus nivolumab 480 mg every 4 weeks, until intolerance or progression.

- ^{17.} Blood for serum and plasma samples will be collected at baseline (D -14), after entinostat lead in (on approximately day 14 (D-1) of entinostat therapy), on week 6, prior to dosing on C2D15, and at the time of the EOT visit. Detailed instructions for blood collection, processing, and storage are provided in the Laboratory Manual.
- ^{18.} Mandatory fresh tissue samples will be collected at D-14 and after entinostat lead-in (on approximately day 14 (D-1) of entinostat therapy prior to dosing on C1D1) and on week 6, prior to dosing on C2D15. A ± 3 day window applies to both time points. All

J1798/Version 5.0/May 21, 2020

samples are collected pre-dose on treatment days). Approximately six (6) core biopsy specimens will be obtained with each biopsy as outlined; the cytopathology slide will also be retained and submitted, if performed (See Section 9.2.1) All

correlative blood/tissue studies should be performed on the same day.

NOTE: If applicable, the daily dose of entinostat may occur prior to hematology/chemistry tests and these laboratory tests may be drawn at the same time as the correlative blood samples.

- ^{19.} A third mandatory biopsy will be performed at week 6 from Cycle 1, Day1. A window of +14 days applies to this time point
- ^{20.} An optional biopsy will be performed at the time of disease progression.
- ^{21.} Archival tumor specimens from previously collected samples will be obtained for correlative analysis, if available.
- ^{22.} Weekly assessments for toxicity/adverse events may occur by phone on days when entinostat alone is administered. Additionally, assessments are to continue for 30 days after the last dose of nivolumab (at intervals <21 days) or to resolution of drug-related AEs to \leq Grade 1, whichever occurs later. SAEs that occur within 100 days of the last treatment or before initiation of a new antineoplastic treatment should also be followed and recorded. These may occur by phone for subjects no longer being seen at the institution; however, an in-person clinic visit may be needed to confirm event resolution and/or to effectively evaluate possible immune-related events. Subjects must be told of follow-up requirements at study entry.
- ^{23.} Subjects who complete or discontinue from treatment because of progression disease will be followed (by phone or email) every three months (+/- 2 weeks) after completion of the EOT visit for up to 2 years or study closure to monitor overall survival. Information of other cancer therapies after discontinuation from the study treatment will also be collected.

For subjects who discontinue treatment for reasons other than tumor progression, will be contacted (by phone or email) every three months (+/- 2 weeks) after completion of the EOT for up to 2 years or study closure to monitor overall survival, and information

93

about disease status will be also collected if possible (i.e. radiological imaging and/or tumor markers) until documented tumor progression.

NOTE: For evaluation of PFS, all subjects who discontinue study drug administration prior to 6 months must have restaging scans/imaging within a 7 day window of the 6 month time point from the date of initiation of combination treatment

J1798/Version 5.0/May 21, 2020

